Appendix B: Responsibilities of the Investigator

Clinical research studies Sponsored by the Sponsor are participant to ICH GCP and all the applicable local laws and regulations.

The Investigator agrees to assume the following responsibilities.

- 1. Conduct the study in accordance with the protocol.
- 2. Personally conduct or supervise the staff who will assist in the protocol.
- 3. Ensure that study related procedures, including study specific (non routine/nonstandard panel) screening assessments are NOT performed on potential participants, prior to the receipt of written approval from relevant governing bodies/authorities.
- 4. Ensure that all colleagues and employees assisting in the conduct of the study are informed of these obligations.
- 5. Secure prior approval of the study and any changes by an appropriate IRB that conforms to local regulatory requirements.
- 6. Ensure that the IRB will be responsible for initial review, continuing review, and approval of the protocol. Promptly report to the IRB all changes in research activity and all anticipated risks to participants. Make at least yearly reports on the progress of the study to the IRB and issue a final report within 3 months of study completion.
- 7. Ensure that requirements for informed consent, as outlined in local regulations, are met.
- 8. Obtain valid ICF from each participant who participates in the study and document the date of consent in the participant's medical chart. Valid informed consent is the most current version approved by the IRB. Each ICF should contain a participant authorization section that describes the uses and disclosures of a participant's personal information (including personal health information) that will take place in connection with the study. If an ICF does not include such a participant authorization, then the Investigator must obtain a separate participant authorization form from each participant or the participant's legally acceptable representative.
- 9. Prepare and maintain adequate case histories of all persons entered into the study, including eCRFs, hospital records, laboratory results, etc., and maintain these data for a minimum of 2 years following notification by the Sponsor that all investigations have been discontinued or that the regulatory authority has approved the marketing application. The Investigator should contact and receive written approval from the Sponsor before disposing of any such documents.
- 10. Allow possible inspection and copying by the regulatory authority of GCP-specified essential documents.
- 11. Maintain current records of the receipt, administration, and disposition of Sponsor-supplied drugs, and return all unused Sponsor-supplied drugs to the Sponsor.
- 12. Report adverse reactions to the Sponsor promptly. In the event of an SAE, notify the Sponsor within 24 hours.

Page 64 of 64 30 Aug 2022

1. INTRODUCTION

The following statistical analysis plan (SAP) provides the framework for the analysis and presentation of the data from this study. Any changes made from the planned analysis described in the protocol or after finalization of this SAP will be documented in the Clinical Study Report (CSR). The section referred to as "Table, Figure, and Listing Shells" within this SAP describes the Clinical Data Interchange Standards Consortium (CDISC) input in order to provide traceability to the corresponding tables, figures, and listings (TFLs). Analysis data model (ADaM) is the source for tables and figures (as well as listings that may contain derived data) and study data tabulation model (SDTM) is the source for the data listings.

Any additional exploratory analyses not addressed within this SAP and/or driven by the data, or requested by Cerevance Beta Inc., will be considered out of scope and must be described in the CSR.

2. OBJECTIVES AND ENDPOINTS

Objectives	Endpoints	
Primary		
To determine the relative bioavailability (BA) of 150 mg of CVN424 administered in a single dose of suspension formulation compared to 150 mg tablet	 The relative bioavailability of the CVN424 suspension in the fasted state, and CVN424 tablet formulation in the fasted and fed state based on maximum observed plasma concentration (Cmax), time to reach Cmax (Tmax), and area under the plasma concentration time curve from time 0 to 96 hours (AUC0-96h) which is the primary area PK parameter. The ratio of the pharmacokinetic (PK) parameters between CVN424 suspension and tablet in the fasted and fed state will be calculated and summarized descriptively. In addition, an analysis of variance (ANOVA) on log-transformed PK parameters (AUC0-1, AUC0-96h, Cmax) will be performed. Ratios of geometric means and 90% confidence intervals will be calculated. Tmax will be compared between CVN424 suspension and CVN424 tablet with and without food. 	

Secondary	
To establish the effects of food (FE) on the rate and extent of absorption of CVN424 150 mg tablet when administered in fed conditions compared to administration under fasting conditions.	• The ratio of the PK parameters between CVN424 tablets in the fed and fasted state will be calculated and summarized descriptively. In addition, an analysis of variance (ANOVA) on log-transformed PK parameters (AUC _{0-t} , AUC _{0-96h} , C _{max}) will be performed. Ratios of geometric means and 90% confidence intervals will be calculated. T _{max} and T _{lag} will be compared between CVN424 tablets in the fed and fasted state.
To assess the safety of the tablet under fast and fed conditions and suspension under fast conditions	• Treatment-emergent adverse events (TEAEs) and tolerability as measured by discontinuations (D/Cs) due to adverse event (AE).
Exploratory*	
Explore serum/plasma (e.g., potential characterization of drug metabolites) that may contribute to variability in CVN424.	Potentially characterize metabolic enzyme and transporter polymorphisms.
Assessment of urine concentrations and volumes to enable calculation of urine PK parameters where possible.	• Urine concentrations and volumes of CVN424 tablet formulation at pre-dose and 0-12, 12-24, 24-48, 48-96 hours post-dose. Urine PK parameters (cumulative amount of unchanged drug excreted into the urine [Ae], fraction of unchanged drug excreted in the urine [fe], and renal clearance [CL _R]) to be determined where possible.

^{*}Metabolites will not be investigated in plasma and urine as part of the SAP. If AUC_{0-t} equals AUC_{0-96h}, only AUC_{0-96h} will be presented.

3. STUDY DESIGN

This study is designed to meet the objective(s) outlined in Section 2.

This is a randomized, open-label, single-oral dose, three-way cross-over study under fasted and fed conditions, in healthy participants.

32 healthy male or female participants will be enrolled in 1 of 6 single-dose, three-way crossover sequences. Sequences 1, 3, 4, and 5 will have 5 participants each, and Sequences 2 and 6 will have 6 participants each. Please see the study schema below:

Dosing #1		Dosing #2		Dosing #3
(Period 1 Day 1)		(Period 2 Day 1)		(Period 3 Day 1)
Suspension (fasted)		Tablet (fasted)		Tablet (fed)
Tablet (fasted)		Tablet (fed)		Suspension (fasted)
Tablet (fed)	hout	Suspension (fasted)	h o u t	Tablet (fasted)
Suspension (fasted)	Was	Tablet (fed)	W a s	Tablet (fasted)
Tablet (fasted)		Suspension (fasted)		Tablet (fed)
Tablet (fed)		Tablet (fasted)		Suspension (fasted)
	(Period 1 Day 1) Suspension (fasted) Tablet (fasted) Tablet (fed) Suspension (fasted) Tablet (fasted)	(Period 1 Day 1) Suspension (fasted) Tablet (fasted) Tablet (fed) Suspension (fasted) Tablet (fasted) Tablet (fasted)	(Period 1 Day 1) (Period 2 Day 1) Suspension (fasted) Tablet (fasted) Tablet (fasted) Tablet (fed) Suspension (fasted) Suspension (fasted) Suspension (fasted) Tablet (fed) Tablet (fasted) Suspension (fasted)	(Period 1 Day 1) (Period 2 Day 1) Suspension (fasted) Tablet (fasted) Tablet (fasted) Tablet (fed) Tablet (fed) Suspension (fasted) Suspension (fasted) Tablet (fed) Tablet (fasted) Suspension (fasted) Suspension (fasted) Suspension (fasted)

Each sequence will proceed through three cross-overs (suspension-fasted, tablet-fed, tablet-fasted) according to the schematic above, with dosing to occur on Day 1 of each of the three periods. Participants in the fasted portion of each sequence will be dosed under overnight fasted conditions and will remain fasted for 4 hours post-dose. Water consumption is permitted as desired except for 1 hour before and after administration of Study Drug.

To assess the effect of food on CVN424 bioavailability in tablet formulation, the single-dose administration will be administered after ingestion of a standardized high-fat, high-calorie meal according to FDA Guidance for Industry (Food-effect (FE) bioavailability and fed bioequivalence studies, Jun 2022).

Participants for all sequences will be admitted to the study unit 1 day prior to dosing and remain in the unit for safety and PK assessments through 96 hours post-dose. The total confinement for each period will be 5 nights per sequence (15 days total) unless extended at the discretion of the Investigator, e.g., for monitoring and/or management of AEs.

Once 96-hour post-dose PK has been collected, participants will be discharged from the unit for the remainder of the washout period and return the day prior to their next scheduled dosing period.

4. ANALYSIS POPULATIONS

Safety Set

The Safety Analysis Set will consist of all participants who are enrolled and receive study drug. Participants in this analysis set will be used for demographic, baseline characteristics, and safety summaries.

Pharmacokinetic Set

The PK set will consist of all participants who receive study drug and have at least 1 measurable plasma concentration.

If any participants are found to be non-compliant with the dosing schedule or with incomplete data, a decision will be made on a case-by-case basis as to their inclusion in the analysis but will be presented in the participant listings.

5. TREATMENT DESCRIPTIONS

Treatment A will be supplied as 150 mg CVN424 suspension.

Treatments B and C will be supplied as 150 mg CVN424 tablets.

For the Suspension (fasted) and Tablet (fasted) portions: Breakfast will not be provided on dosing days. Participants must fast for a minimum of 4 hours after dose administration unless otherwise indicated. CVN424 will be administered with approximately 240 mL of water after a fast of at least 10 hours. Participants will continue to fast for an additional 4 hours after dosing and eat lunch following the 4-hour PK blood collection. Participants may consume water ad libitum except for 1 hour before and 1 hour after drug administration.

For the Tablet (fed) portion (food effect): CVN424 will be administered after ingesting a standardized high-fat, high-calorie meal according to FDA Guidance for Industry (Foodeffect bioavailability and fed equivalence studies, June 2022). Participants will finish their breakfast in its entirety within 30 minutes and will receive an investigational product 30 minutes (±5 minutes) after beginning the meal. The meal start and stop times, and percentage of the meal consumed will be recorded in the source, and the appropriate case report form (CRF) for all meals served on dosing days.

The treatments descriptions would be described as:

Treatment	Short Description	Long Description
Treatment A	Suspension-Fasted	a single oral dose of 150 mg CVN424 suspension under fasted condition

Treatment	Short Description	Long Description
Treatment B	Tablet-Fasted	a single oral dose of 150 mg CVN424 tablet under fasted condition
Treatment C	Tablet-Fed	a single oral dose of 150 mg CVN424 tablet under fed condition

6. PHARMACOKINETIC ANALYSIS

6.1 Investigational Product and Pharmacokinetic Analyte Information

The analyte, CVN424, can be described with the following structure and molecular weight (MW) of 473.52 g/mol (Figure 6-1).

Plasma and urine CVN424 concentrations will be analyzed. As the amount of CVN424 to be dosed corresponds to the described dose, no corrections will be needed for any dosedependent PK parameters.

Figure 6-1: CVN424 (MW = 473.52 g/mol)

6.2 Bioanalytical Method

Plasma and urine concentrations of CVN424 will be determined using high performance liquid chromatography-tandem mass spectrometry (HPLC/MS-MS) method validated with respect to accuracy, precision, linearity, sensitivity, and specificity at Frontage Laboratories, Inc. The analytical range (lower limit of quantitation [LLOQ] – upper limit of quantitation [ULOQ]) for CVN424 in plasma and urine are both expected to be 1 – 1000 ng/mL.

6.3 Pharmacokinetic Concentrations

Measurements and Collection Schedule

Collection of Blood for PK Sampling

Blood samples for analysis of CVN424 plasma concentrations will be collected into chilled Vacutainers containing K₂EDTA. Instructions for sample processing and shipment are

provided in a separate lab manual. In all treatments, serial blood samples to determine CVN424 concentrations in plasma will be collected according to the Schedule of Study Procedures. The PK samples will be collected at the nominal time point: Predose (within 15 minutes prior to dosing; 60 minutes for the fed treatments), 0.5, 1, 1.5, 2, 3, 4, 6, 8, 12, 16, 24, 36, 48, 60, 72, 84 and 96 h; all other assessments will be collected, before or after, within the allowable windows. The actual time of sample collection will be recorded on the source document and CRF. Sampling time points may be adjusted or added based on the preliminary emerging PK data collected from prior sequence(s).

Collection of Urine for PK Sampling

In Tablet-Fasted treatment only, urine samples for analysis of CVN424 (or its metabolites) concentration in urine will be collected: pre-dose (within 12 hours prior to dosing), 0-12, 12-24, 24-48, and 48-96-hours post-dose. Volume of urine collected is to be recorded. Instructions for sample processing and shipment are provided in a separate lab manual.

All concentration data will be listed by participant, treatment, and nominal time in an appendix. If there are any significant protocol deviations (e.g., significant time deviations from nominal sample times), some individual concentration data may be excluded from mean data presentations (e.g., descriptive statistics for concentrations at specific nominal time points and mean concentration-time plots). All deviations and excluded data will be provided and discussed in the CSR.

6.4 Noncompartmental Pharmacokinetic Analysis and Parameter Calculation

6.4.1 Plasma Pharmacokinetic Parameters

Plasma concentrations of CVN424 as determined per the bioanalytical method and the collection times described in Section 6.2 and Section 6.3, respectively, will be used for the calculation of the plasma CVN424 PK parameters.

The appropriate noncompartmental PK parameters will be calculated from the plasma CVN424 concentration-time data using Phoenix® WinNonlin® Version 8.3.4 or higher. Actual sample times will be used in the calculations of the PK parameters. The calculation of the actual time for CVN424 will be in respect to the dose administration time of CVN424 on Day 1. All PK parameters included in the protocol are listed in Table 6–1 below, and are defined as appropriate for study design.

Table 6–1 Noncompartmental Plasma CVN424 Pharmacokinetic Parameters to be Calculated

Parameter	Label to be Used in the Text, Tables, and Figures	Definition	Method of Determination
AUC _{0-inf}	AUC0-inf	Area under the concentration-time curve from time 0 extrapolated to infinity	$\begin{aligned} &AUC_{0\text{-inf}}\\ &=AUC_{0\text{-t}}+\left(C_{last}/Kel\right)\\ &\text{where Clast is the last}\\ &\text{observed/measured}\\ &\text{concentration} \end{aligned}$
AUC _{0-t}	AUC0-t	Area under the concentration-time curve from time 0 to the time of the last observed/measured non-zero concentration	Calculated using the Linear Trapezoidal with Linear Interpolation Method
AUC _{0-96h}	AUC0-96h	Area under the concentration-time curve from time 0 to 96 hours postdose. This parameter may be interpolated or extrapolated (primary PK area parameter).	Calculated using the Linear Trapezoidal with Linear Interpolation Method
AUC%extrap	AUC%extrap	Percent of AUC _{0-inf} extrapolated, represented as (1 - AUC _{0-i} /AUC _{0-inf})*100	$\begin{array}{l} AUC_{\text{%extrap}} = \\ (1-AUC_{0-t}/AUC_{inf}) \ x \ 100 \end{array}$
C_{max}	Cmax	The maximum observed concentration	Taken directly from bioanalytical data
CL/F	CL/F	The apparent total plasma clearance after oral administration	CL/F = Dose/(AUC _{0-inf})
K _{el}	Kel	Apparent first-order terminal elimination rate constant	Calculated by linear least-squares regression analysis using the maximum number of points in the terminal log-linear phase (e.g., 3 or more non-zero concentrations)
T_{lag}	Tlag	Lag time – the time delay between drug administration and the onset of absorption; where onset of absorption could be defined as the time point prior to the first observed/measured non-zero plasma concentration.	Taken from clinical database as the difference in the time of administration and the time of the associated blood draw. Report actual time per individual, as opposed to nominal time.
T _{max}	Tmax	The time to reach C_{max} ; if C_{max} occurs at more than one time point, T_{max} is defined as the first time point with this value	Derived from clinical data as the difference in the time of the blood draw which is associated with the C _{max} and the time of administration
$t_{1/2}$	t½	Apparent first-order terminal elimination half-life	$t\frac{1}{2} = 0.693/\text{Kel}$

Parameter	Label to be Used in the Text, Tables, and Figures	Definition	Method of Determination
V _z /F	Vz/F	The apparent volume of	$V_z/F =$
		distribution during the terminal	$Dose/(AUC_{0-inf} \times Kel)$
		elimination phase after oral	
		administration	

^{*}In the text of the CSR, subscripts will be used in parameter names, as appropriate. However, in post-text tables and listings, subscripts will not be used in parameters. AUC_{0-inf} will not be discussed in CSR and will not be presented in in-text tables. If AUC_{0-t} equals AUC_{0-96h} , then only AUC_{0-96h} will be presented and the corresponding footnote will be added.

PK parameters will not be calculated for participants with less than 3 consecutive postdose time points with quantifiable concentrations. Participants for whom there are insufficient data to calculate the PK parameters will be included in the concentration tables and individual concentration-time figures only and excluded from the summaries and statistical analysis.

For the calculation of the PK parameters, plasma concentrations below the limit of quantitation (BLQ) prior to the first quantifiable concentration will be set to 0 and plasma concentrations BLQ after the first quantifiable concentration will be treated as missing.

The K_{el} will be determined using linear regressions composed of at least 3 data points. Furthermore, the K_{el} will not be assigned if 1) the terminal elimination phase is not apparent, 2) T_{max} is one of the last 3 data points, or 3) the R² value is less than 0.75. In cases where the Kel interval is not assigned, the values of K_{el} and K_{el}-dependent parameters (i.e., t_½, AUC_{0-inf}, CL/F, and V_z/F) are considered not calculable and will not be reported. Wherever the resulting t_½ is more than half as long as the sampling interval, the Kel value and Kel-dependent parameters (i.e., t_½, AUC_{0-inf}, CL/F, and V_z/F) may be flagged and presented, as judged appropriate and in accordance with Celerion SOPs.

Wherever the AUC% is greater than 20%, the K_{el} value and K_{el} -dependent parameters (i.e., $t\frac{1}{2}$, AUC0-inf, CL/F, and V_z/F) will not be reported.

All available data will be included in the concentration and PK parameter tables to the extent possible. Data for each participant will be included in the summary statistics and statistical comparisons of PK parameters with the exceptions described as follows:

- Data from participants who experience emesis at or before 2 times median T_{max} for the given treatment during the PK sampling period time course of the study for CVN424 will be excluded from the summary statistics and statistical comparisons of PK parameters for the given treatment.
- Data from subjects who violate a protocol inclusion or exclusion criteria or deviate from the protocol define procedures that are deemed important a priori, or have unavailable or incomplete data which may influence the PK analysis will be excluded from the summary

statistics and statistical comparisons of PK parameters (entirely or for a given treatment, as appropriate).

• If predose concentrations > 5% of Cmax are observed, the affected participant's concentration and PK parameter data will be excluded from the summary statistics and statistical comparisons of PK parameters for the given treatment.

6.4.2 Urine Pharmacokinetic Parameters

The following PK parameters will be calculated from urine CVN424 data using Phoenix[®] WinNonlin[®] and SAS[®]. All PK parameters included in the protocol are listed in Table 6–2 below, and are defined as appropriate for study design.

Table 6-2 Noncompartmental Urine Pharmacokinetic Parameters to be Calculated

Parameter	Label to be Used in Text, Tables, and Figures	Definition	Method of Determination
Ae, _{t1-t2}	Ae,t1-t2	Amount of CVN424 excreted in each postdose urine collection interval (t1 to t2, t2 to t3, etc.)	$Ae,t1-t2 = (Cur,t1-t2 \times Vur, t1-t2)$
Ae	Ae	Cumulative amount of CVN424 excreted in the urine through urine collection interval	Calculated as: Ae = Ae,t1-t2 + Ae,t2-t3 + $Ae,t(n-1)-tn$ where $t1 = 0$ and $tn = the$ end of the last collection interval
fe	fe	Fraction of dose excreted CVN424 into urine within each postdose urine collection interval	Calculated as [Ae]/Dose
CL _R	CL_{R}	Renal clearance (overall interval only)	CLr = Ae/AUC where Ae (urine) and AUC (plasma) are determined over a time-matched interval (i.e., from time 0 to the latest interval with quantifiable concentrations in both urine and plasma, by participant)

^{*}In the text of the CSR or report, subscripts will be used in parameter names, as appropriate.

For the calculation of urine PK parameters, urine concentrations BLQ will be set to zero (0) and the amount and fraction excreted in the urine for the respective collection interval will be estimated as zero (0). Cumulative urine PK parameters (e.g., Ae) and derived parameters (e.g., fe) after a missing sample (e.g., lost part of void, volume not recorded) will be presented (as underestimated), but may be excluded from summary statistics, if warranted. In

the case of no void during a given interval, cumulative parameters and derived cumulative parameters will be carried forward from the previous (postdose) interval to the given interval (or set to zero [0] if there is not a previous postdose interval with quantifiable data).

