Appendix 16.2.5.8 Pharmacokinetic Urine Collection (Safety Set)

Urine Collection

				CRF (Collection		 Start	 9	top	- Analyte>	Urine	
Study Sequenc	Subject e Number		Treatment			Date	Time	Date	Time	- Concentration (units)	Weight (g)	Comments
1	1	1	В	1 0	-1.50 .00 - 4.00	DDMONYYYY DDMONYYYY	HH:MM:SS HH:MM:SS	DDMONYYYY DDMONYYYY	HH:MM:SS HH:MM:SS	XXXX XXXX	X.XX X.XX	No void Unknown amount of urine spilled
			\Diamond	4 48	.00 - 96.00	<similar t<="" td="">o above for	all time p	oints and s	subjects>			</similar>	o above for	all time p	oints and s	subjects>		

Treatment B: < >

Program: /CAXXXXX/sas_prg/pksas/standardlis/pk_urn.sas DDMMMYYYY HH:MM

Programmer Notes:

- Population: Safety set will be used in this listing.
- If SS are not present, then Time may be presented as HH:MM.

Page X of X Table CPKell Intervals (Hours) Used for Determination of Plasma CVN424 Kel Values (Pharmacokinetic Set)

Subject	Treatment	Treatment			Treatment		
Number	Sequence	Interval	R2 	n 	Interval	R2 	n
X	XX	XX.X - XX.X	X.XXX	X	XX.X - XX.X	X.XXX	X
X	XX	XX.X - XX.X	X.XXX	X	XX.X - XX.X	X.XXX	X
X	XX	XX.X - XX.X	X.XXX	X	XX.X - XX.X	X.XXX	X
X	XX	XX.X - XX.X	X.XXX	X	XX.X - XX.X	X.XXX	X
X	XX	XX.X - XX.X	X.XXX	X	XX.X - XX.X	X.XXX	X
X	XX	XX.X - XX.X	X.XXX	X	XX.X - XX.X	X.XXX	X

R2 = Coefficient of determination

n = Number of points used in Kel calculation

Notes for Generating the Actual Table:

Treatmen columns: Suspension-Fasted, Tablet-Fasted, Tablet-Fed

Presentation of Data:

- Interval start and stop times will be presented to 1 decimal or 3 sig figures min;
- R2 will be presented to 3 decimals;
- n will be presented as an integer (with no decimal)

Programmer note:

Use long treatment descriptions for footers

Program: /CAXXXXX/sas_prg/pksas/adam_kel.sas DDMMMYYYY HH:MM

^{. =} Kel value not reportable.

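### SAP 6.4.2: renal clearance is biased low in any participant with an incomplete urine collection inside the Ae/AUC window, although samples already taken allow a matched estimate

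*SAP*

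**What the plan says.** The CLR row of SAP Table 6-2 sets CLR = Ae/AUC, with both taken over a time-matched interval. It then defines that interval as a single window "from time 0 to the latest interval with quantifiable concentrations in both urine and plasma, by participant". Ae is defined as "Cumulative amount of CVN424 excreted in the urine through urine collection interval", that is, the running sum of the interval amounts from time 0. CLR is reported for the overall interval only.

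For a missing sample, SAP 6.4.2 gives two examples: part of a void lost, and a volume not recorded. Cumulative parameters and those derived from them then "will be presented (as underestimated), but may be excluded from summary statistics, if warranted". The examples named are Ae and fe; CLR is not mentioned, although it is derived from Ae. An interval with no void is handled separately, by carrying the cumulative amount forward.

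Two other rules bear on this. SAP 6.4.1, the plasma section, says that data from participants who "have unavailable or incomplete data which may influence the PK analysis will be excluded from the summary" statistics and comparisons. SAP 6.5 says that excluded participants stay in the urine tables, are left out of the summary statistics, and are noted as such.

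Urine is collected after the fasted tablet only, at "0-12, 12-24, 24-48, and 48-96-hours post-dose" (SAP 6.3). Plasma is sampled at "0.5, 1, 1.5, 2, 3, 4, 6, 8, 12, 16, 24, 36, 48, 60, 72, 84 and 96 h".

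**The concern.** Ae and AUC in a clearance ratio must cover the same time. Under the written window, the end point depends on whether concentrations are quantifiable, not on whether the urine was fully collected. A collection can yield a quantifiable concentration and still have an unrecorded volume or a part-lost void. Its missing amount then leaves the numerator, while its plasma AUC stays in the denominator. The resulting CLR is too low, and the error never goes the other way.

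Overall Ae and fe cannot be repaired after a loss, because they need the total excreted. CLR can, because a ratio over the remaining complete intervals estimates the same quantity. As written, the plan either reports a value known to be low or drops the participant. What is at stake is one of the three urine parameters in the exploratory objective (Protocol 5.1; SAP 2).

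**Working it through.** The documents give no figure for CLR or for this bias, so there is nothing to reproduce.

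**Inputs**
- Urine intervals 0-12, 12-24, 24-48 and 48-96 h, and the plasma sampling grid: SAP 6.3.
- AUC by the linear trapezoidal rule: SAP Table 6-1.
- Terminal half-life of about 33 h and median Tmax of 1.5 h: Protocol 4.1. The half-life is reported with repeated once-daily dosing and the Tmax is for the fasted suspension, so both are assumptions for a single fasted tablet dose.
- Planned enrolment of 32: Protocol 11.3.
- Curve shapes: assumed.

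**Step 1, algebra.** If CLR is constant over time, each interval amount is Ae_i = CLR × AUC_i. If the whole of interval j is lost while the window still runs to 96 h:

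SAP value = CLR × (1 − AUC_j / AUC0-96)

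The proportional shortfall is that interval's share of AUC0-96. If half the interval's amount is lost and the rest is counted, the shortfall is half that share.

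**Step 2, mono-exponential curve.** With k = ln 2 / 33, the share of an interval from a to b is [exp(−ka) − exp(−kb)] / [1 − exp(−96k)]. For 0-12 h this is (1 − 0.7772) / (1 − 0.1331) = 0.2228 / 0.8669 = 0.257.

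| Interval | Shortfall, whole interval lost | Shortfall, half lost |
|---|---|---|
| 0-12 h | 25.7% | 12.9% |
| 12-24 h | 20.0% | 10.0% |
| 24-48 h | 27.6% | 13.8% |
| 48-96 h, concentration quantifiable | 26.7% | 13.4% |

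**Step 3, other curves.** I put a one-compartment oral curve (half-life 33 h, Tmax 1.5 h) through the linear trapezoid on the SAP sampling grid. I then varied it: half-life 20 and 45 h, Tmax 4 h, and two biexponential curves with a 3 h first phase. The last column covers all six curves.

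| Whole interval lost | Share of AUC0-96, base curve | SAP CLR as % of true, base curve | SAP CLR as % of true, all curves |
|---|---|---|---|
| 0-12 h | 25.2% | 74.7% | 57-79% |
| 12-24 h | 20.1% | 79.8% | 76-83% |
| 24-48 h | 27.8% | 72.1% | 72-79% |

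The shortfall across these three intervals is therefore about 17% (100 − 83) to 43% (100 − 57). Losing half of one of them leaves 86-90% of the true value on the base curve. The 48-96 h interval holds 26.9% of AUC0-96 on the base curve and 16.1-32.5% across all curves. An unrecorded volume there, with a quantifiable concentration, costs roughly that share.

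**Step 4, last sample wholly absent.** The latest interval quantifiable in both matrices is then 24-48 h, so numerator and denominator both stop at 48 h. The base curve gives 99.97% of the true value, so there is no bias.

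**Step 5, matched intervals.** Plasma samples fall at 12, 24, 48 and 96 h, so the AUC of every urine interval is available. Dropping the lost interval from both sums gives 98.9-100.0% of the true CLR across all the curves. A participant with complete urine gets 99.4-100.0%; the small remaining gap is trapezoid error.

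**Step 6, effect on the mean.** If 3 of 32 participants lose the whole 0-12 h collection and stay in the summary, mean CLR falls by 3/32 × 25.2% = 2.4%. For 8 of 32 it falls by 8/32 × 25.2% = 6.3%. These counts are illustrations; the documents give no loss rate.

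**The case against.** The strongest case against is that the plan already deals with this. SAP 6.4.2 labels the affected values as underestimated and permits their exclusion. The incomplete-data rule in SAP 6.4.1 is mandatory in wording, SAP 6.5 shows how exclusions are displayed, and SAP 4 allows case-by-case decisions. A reader might infer that the plan would pass off a hidden bias as a valid result; the documents do not support that. What remains is narrower. The exclusion in 6.4.2 is discretionary, has no criterion, and does not name CLR. The 6.4.1 rule sits in the plasma section. Above all, exclusion removes a value that could have been recovered, and no rule corrects it.

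It can also be said that the CLR row asks for time-matched quantities, so a careful analyst would not pair a gap in Ae with a full AUC. The aim is indeed right, but the definition that follows is one unbroken window from time 0, and following it breaks the match. The plan needs the definition to agree with the aim.

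The urine listing shell carries the comment "Unknown amount of urine spilled", which might be read as a sign that spills are expected here. It is template text. The same shell shows a 0-4 h collection that this trial does not have, and SAP 11 says the shells may not reflect every aspect of the study. Participants are confined through 96 h, so collection takes place in the unit. The case for a rule rests on SAP 6.4.2 itself providing for missing samples.

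**Conclusion.** The point stands as an inexpensive improvement to an exploratory parameter. Under the written definition, any incomplete collection inside the window biases that participant's CLR low, whichever interval it is. The exception is a wholly absent last sample.

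The size depends on assumed curves and on how much urine is lost. The 20-28% figure is for a whole interval on one mono-exponential curve with a 33 h half-life. A reader might apply it to a spill, but a part-lost void costs less: about 10-14% if half of an interval's amount is lost. Nor is 20-28% the outer range for a whole interval, since other plausible curves give about 17-43% for the first three intervals. The effect on the mean would be a few per cent unless losses were common.

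A reader might also infer that the trial's main conclusions are at risk. They are not: CLR is exploratory, is measured after the fasted tablet only, and has no decision criterion attached. The matched-interval value is not free of assumptions either. It needs renal clearance to be constant over time, as does an overall Ae/AUC.

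**What to change.** Reword the CLR row of SAP Table 6-2: CLR is the sum of the interval amounts Ae,t1-t2 over intervals with complete urine collection, divided by the sum of the plasma partial AUCs over those same intervals. State that a partly lost interval is dropped from both sums, and that a confirmed no-void interval counts as complete with zero excretion. State the constant-CLR assumption.

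For participants with an incomplete interval, replace the optional exclusion with a fixed rule: overall Ae and fe are listed, and are excluded from summary statistics.

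The cost is SAP wording and partial AUCs from plasma concentrations already collected; the interval amounts are already planned. The downside is that CLR in affected participants rests on fewer intervals. Setting CLR to missing after an incomplete collection would be simpler and would also avoid the bias, but it gives up the recoverable value.
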